2.4 PK BLOOD SAMPLES FLOW CHART

| CYCLE | STUDY VISIT | DAY | NR. PK SAMPLES | TIMING ¹ |
|-------|-------------|-----|----------------|---|
| 1 | 1 | 1 | 10 | Pre-infusion |
| | | | | At the end of infusion |
| | | | | 1 h after the end of infusion |
| | | | | 2 h after the end of infusion |
| | | | | 4 h after the end of infusion |
| | | | | 6 h after the end of infusion |
| | | | | 8 h after the end of infusion |
| | | | | 10 h after the end of infusion |
| | | | | 12 h after the end of infusion |
| | | | | 16 h after the end of infusion |
| 2 | 2 | 2 | 2 | 24 h after the end of infusion |
| | | 3 | 1 | 36 h after the end of infusion |
| | | 4 | 1 | 48 h after the end of infusion |
| | | 8 | 1 | 72 h after the end of infusion |
| 3 | 3 | 8 | 1 | At the time of safety lab tests* |
| | | 15 | 1 | At the time of safety lab tests* |
| 2 | 1 | 1 | 10 | Pre-infusion |
| | | | | At the end of infusion |
| | | | | 1 h after the end of infusion |
| | | | | 2 h after the end of infusion |
| | | | | 4 h after the end of infusion |
| | | | | 6 h after the end of infusion |
| | | | | 8 h after the end of infusion |
| | | | | 10 h after the end of infusion [§] |
| | | | | 12 h after the end of infusion [§] |
| | | | | 16 h after the end of infusion [§] |
| 3+ | 2 | 2 | 2 | 24 h after the end of infusion |
| | | | | 36 h after the end of infusion |
| | | | | 48 h after the end of infusion |
| | | | | 72 h after the end of infusion |
| | | | | At the time of safety lab tests* |
| 3+ | 3 | 15 | 1 | At the time of safety lab tests* |
| | | | | Pre-infusion |
| | | | | At the end of infusion |
| | | | | At the time of safety lab tests |
| | | | | At the time of safety lab tests |

¹ ONLY for dose levels higher or equal to 0.80 mg/kg, in case additional sampling for safety test is required (e.g., between study visits), an additional blood sample for PK will be taken at the same time.

* PK blood samples will be taken ONLY for dose levels higher or equal to 0.80 mg/kg.

§ PK blood sampling at 10, 12 and 16 hours after the end of infusion is not mandatory.

NOTE: If any interruption occurs during MEN1309 infusion at any cycle, an additional blood sampling for PK will be taken at the time of each infusion interruption and just before each infusion resumption.

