NOTE: safety laboratory tests performed within 24 hours prior to Day 1 are accepted and do not need to be repeated at Visit 1 (Day 1) prior to study drug administration.

- Dose Cohort assignment
- PK blood sampling (pre-infusion)
- Tumor Lysis Syndrome (TLS) risk assessment according to Investigator's TLS manual (see Appendix II)
- TLS prophylaxis if applicable (see Appendix II)
- Premedication
- Recording of AEs and change in concomitant medication

Study drug administration

- Study drug administration, given as a 3-hour IV infusion
- Vital signs every 15 minutes during the first hour of study drug administration and then at every hour until the end of infusion. In case of temporary infusion interruption, vital signs should continue to be collected every 15 minutes until the first hour post-infusion re-start and then every hour until the end of infusion (or until 1-hour after the permanent infusion interruption)
- Continuous ECG monitoring during the IV infusion up to 30 minutes after the end of infusion and 12-lead ECG record 30 minutes after the end of infusion
NOTE: If ECG monitoring equipment is not available, heart rate should be monitored up to 30 minutes after the end of infusion and 12-lead ECG recorded at 30, 60 and 120 minutes during the IV infusion with final 12-lead ECG record at 30 minutes after the end of infusion.
- PK blood sampling at the end of infusion, and at 1, 2, 4, 6, 8, 10, 12, and 16 hours after the end of infusion

Day 2, Day 3, and Day 4

Post study drug administration

- Physical examination, including vital signs
- Blood sampling and urine collection for safety lab tests
- PK blood sampling at 24, 36, 48, and 72 hours after the end of infusion
- Recording of AEs (until visit completion) and change in concomitant medications

Visit 2 (Day 8 + Haematology lab test at Day 11)

- Physical examination, including vital signs
- ECOG PS evaluation
- Blood sampling and urine collection for safety lab tests
- Blood sampling for PK only for dose levels ≥ 0.80 mg/kg
- Recording of adverse events and change in concomitant medications

On Day 11, blood sampling for haematology lab test shall be repeated

Visit 3 (Day 15 + Haematology lab test at Day 18)

- Physical examination, including vital signs
- ECOG PS evaluation
- Blood sampling and urine collection for safety lab tests
- Blood sampling for PK only for dose levels ≥ 0.80 mg/kg
- Recording of adverse events and change in concomitant medications

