- The total dose calculated for the first study drug administration has to be also applied for the following ones, provided that the actual patient's weight is within \pm 10% of the weight measured prior to the first study drug administration; otherwise, the total dose to be given shall be calculated based on the weight measured at the corresponding visit.
- The administration of the study drug should only be carried out in a facility in which resuscitation equipment and medical personnel trained in the treatment of anaphylaxis and TLS are immediately available.
- Starting from Cycle 3, the dose of dexamethasone can be adjusted upon Investigator's judgment.
- Starting from Cycle 2, blood sampling for haematology lab test at Day 11 and Day 18 shall be performed if clinically needed.
- If any interruption occurs during MEN1309 infusion at any cycle, an additional blood sampling for PK will be taken at the time of each infusion interruption and just before each infusion resumption.
- ONLY for dose levels higher or equal to 0.8 mg/kg, PK blood samples will be taken at Visits 2 and 3 of each cycle in conjunction with safety blood samples; in case additional samples will be required between study visits for safety reasons, an additional PK sample will be collected.

End of Study Visit (within 6 weeks after the last administered dose or at the time of study withdrawal/treatment discontinuation of study drug)

- Tumor assessment using RECIST v1.1 for Step 1 based on CT scan or MRI and NHL assessment using Cheson Criteria (The Lugano Classification, 2014) for Step 2 based on CT/(PET)-CT scan or MRI
- Physical examination and vital signs
- 12-lead ECG record
- ECOG PS evaluation
- Blood sampling and urine collection for safety lab tests, including β -HCG pregnancy testing
- Blood sampling for immunogenicity assessment
- Blood sampling for free CD205 assessment
- Recording of adverse events and change in concomitant medications

NOTE:

All patients shall undergo the End of Study Visit at the scheduled date within 6 weeks after the last administered dose or at the time of study withdrawal/treatment discontinuation of study drug. Unscheduled assessments showing disease progression and leading to patient's withdrawal can replace the End of Study Visit provided that all assessment/procedures scheduled for this Visit are completed.

Survival Follow-up (up to a period of 12 months after last patient in)

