8.5.3 Pharmacokinetics Procedure and Assessment

Blood samples for MEN1309, tAb, DM4 and its metabolite S-methyl-DM4 serum concentration measurements will be taken before (pre-dose) and immediately after the end of each IV infusion during all cycles for each cohort. If any interruption occurs during MEN1309 infusion at any cycle, an additional blood sampling for PK will be taken at the time of each infusion interruption and just before each infusion resumption.

Furthermore, blood sampling for PK are obtained at 1, 2, 4, 6, 8, 10, 12, 16, 24, 36, 48, and 72 hours after the end of the infusion of Cycle 1 and Cycle 2 (see §2.4). For Cycle 2, PK blood sampling at 10, 12 and 16 hours after the end of infusion is informative but not mandatory.

For Cycles 3+, PK blood samples will be taken only before the start of infusion and immediately after the end of infusion, as well as in conjunction with any safety blood samples taken up to 72 hours after the end of infusion.

For dose levels higher or equal to 0.8 mg/kg, in case additional sampling for safety testing is required (e.g., between study visits), an additional blood sample for PK will also be taken at the same time. Moreover, only for dose levels higher or equal to 0.8 mg/kg, PK blood samples will be taken at Visits 2 and 3 of each cycle in conjunction with safety blood samples (see § 2.4).

The following pharmacokinetic parameters will be determined from the individual serum concentration-time curve for MEN1309, tAb, DM4 and its metabolite S-methyl-DM4, when applicable, using non-compartmental methods with Phoenix™ WinNonlin® software, version 6.4 or higher (Pharsight Corp., Mountain View, California).

| | |
|---------------------|--|
| C_{\max} | Maximum observed serum concentration. |
| t_{\max} | Time to C_{\max} . |
| C_{last} | Last quantifiable serum concentration value. |
| t_{last} | Time to C_{last} . |
| C_{trough} | Pre-dose serum concentration. |
| k_e | Apparent terminal elimination rate constant, estimated by log-linear regression analysis on serum concentrations visually assessed to be on the terminal log-linear phase. |
| $t_{1/2}$ | The terminal serum half-life, calculated according to the following equation: |
| | $t_{1/2} = \frac{0.693}{k_e}$ |
| $AUC_{(0-t)}$ | Area under the serum concentration-time curves from time zero (pre-dose) to the time of the last quantifiable concentration, calculated by means of the linear-log trapezoidal method. |

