| $AUC_{(0-\infty)}$ | Area under the serum concentration-time curve from time zero to infinity, calculated according to the following equation: |
| | $AUC_{(0-\infty)} = AUC_{(0-t)} + \frac{C_{\text{last}}}{k_e}$ |
| $\%AUC_{\text{ex}}$ | The percentage of $AUC_{(0-\infty)}$ obtained by extrapolation calculated as follows: |

$$AUC_{\text{ex}}(\%) = \frac{AUC_{(0-\infty)} - AUC_{(0-t)}}{AUC_{(0-\infty)}} * 100$$

| | |
|---------------------|--|
| CL | Systemic clearance, calculated according to the following equation: |
| | $CL = \frac{Dose}{AUC_{(0-\infty)}}$ |
| V_{ss} | Volume of distribution at steady state, calculated according to the following equation: |
| | $V_{ss} = CL * MRT$ |
| V_d | Volume of distribution based on the terminal phase, calculated according to the following equation: |
| | $V_d = \frac{Dose}{k_e * AUC_{(0-\infty)}}$ |
| $AUMC_{(0-\infty)}$ | The area under the first moment curve from zero to infinity calculated using the equation: |
| | $AUMC_{(0-\infty)} = \sum_{i=0}^{n-1} \frac{t_{i+1} - t_i}{2} (C_i t_i + C_{i+1} t_{i+1}) + \frac{t * Ct}{k_e} + \frac{Ct}{k_e^2} + \frac{t \cdot C_t}{\tau} + \frac{C_t}{\tau^2}$ |
| MRT | Mean residence time was calculated as: |
| | $MRT = AUMC_{(0-\infty)} / AUC_{(0-\infty)}$ |
| Ro | Accumulation ratio following 2 consecutive infusions calculated as: |
| | $Ro = AUC_{(0-t)}^{2nd} / AUC_{(0-t)}^{1st}$ |

PK parameters will be calculated after the first and second infusion of each dose cohort. C_{max} and C_{trough} will also be obtained after each administration of MEN1309. Actual PK sampling times will be used in the derivation of PK parameters. Alternatively, it is also acceptable to consider the planned sampling times if they do not deviate by more than 5% from the actual. Planned sampling times may be used as a replacement for unknown or missing actual times.

The calculation of the parameters listed above and others will depend upon the results of the drug concentration assay and the duration of drug infusions.

For the calculation of individual PK parameters, values Below the Lower Limit Of Quantification (BLOQ) will be handled as follows:

1. BLOQ values located before the t_{max} of their affiliating curve will be transformed to zero.
2. If a BLOQ value located after the t_{max} falls between 2 quantifiable concentrations, it will be omitted from the PK analysis.

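### Protocol 8.5.3 lets planned sampling times replace known actual times within 5%, with no cap in hours and no criterion; this can only add error to ke and half-life, and deleting it costs nothing.

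*Protocol*

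**What the plan says.** Protocol 8.5.3 gives three consecutive rules for the times used in the PK calculation:

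- Default: "Actual PK sampling times will be used in the derivation of PK parameters".
- Option: "it is also acceptable to consider the planned sampling times if they do not deviate by more than 5% from the actual".
- Missing data: "Planned sampling times may be used as a replacement for unknown or missing actual times".

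Nothing says who chooses the option, when, or whether the choice is made by sample, patient or cohort. The tolerance is purely relative.

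The last samples with a planned hour are those at "24, 36, 48, and 72 hours after the end of the infusion of Cycle 1 and Cycle 2". Beyond that, "only for dose levels higher or equal to 0.8 mg/kg, PK blood samples will be taken at Visits 2 and 3 of each cycle". The chart in Protocol 2.4 times these later draws only as "At the time of safety lab tests", and Protocol 8.5.1 fixes the day but no hour.

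Protocol 8.5.3 estimates ke by log-linear regression on points judged by eye to be terminal. Half-life, Vd and the extrapolated part of AUC are derived from it. The SAP (5.1.1.5 and the pharmacokinetics text in 6.1.1.2) lists the parameters and summary statistics but does not mention sampling times or the 5% rule.

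**The concern.** The 5% condition can be checked only if the actual time is known. When it is not known, the third rule applies. The option therefore only ever replaces a recorded time with a less accurate one.

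A relative limit also widens with time: 3 minutes at 1 h, 3.6 h at 72 h, and more for later samples if a nominal hour is assigned to them. Late points have the most leverage on a terminal slope. The error need not average out across a cohort, because a site whose infusions end in the afternoon and whose visits are in the morning is off in the same direction for every patient.

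At stake is the accuracy of ke, half-life and Vd, and whether two analysts with the same data would report the same values. Protocol 6.2.2.3.2 reports dose-dependent half-life and clearance in monkeys, so comparing these parameters across small dose cohorts is of real interest here.

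**Working it through.** The documents give no error figure on this point, so there is none to reproduce.

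**Inputs.** The 5% tolerance and the 24, 36, 48 and 72 h samples are from Protocol 8.5.3. Day 8 and Day 15 are from Protocol 8.5.1; placing them at 168 h and 336 h is an assumption. The decline is assumed mono-exponential over the terminal points.

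**Step 1: time tolerance.** The condition |planned − actual| ≤ 0.05 × actual puts the actual time between planned/1.05 and planned/0.95.

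- 72 h: 68.6 to 75.8 h (5% of 72 = 3.6 h).
- 168 h, assumed: 160.0 to 176.8 h (5% = 8.4 h).
- 336 h, assumed: 320.0 to 353.7 h (5% = 16.8 h).

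**Step 2: shift in ke.** If ln C falls linearly in actual time a but is regressed on planned time p, then

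estimated ke / true ke = Σ(p − p̄)a / Σ(p − p̄)².

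This ratio does not depend on the half-life. For 72/168/336 h, p̄ = 192, the deviations are −120, −24 and 144, and Σ(p − p̄)² = 35,712. The worst cases have the early and late points off in opposite directions:

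- Actual 75.79, 176.84, 320.0 h: (−9,094.7 − 4,244.2 + 46,080)/35,712 = 0.917.
- Actual 68.57, 160.0, 353.68 h: (−8,228.6 − 3,840 + 50,930.5)/35,712 = 1.088.

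The same search over other terminal sets gives:

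| Terminal points (h) | ke, worst case | Half-life, worst case |
|---|---|---|
| 24, 36, 48, 72, 168, 336 | −6.3% to +6.8% | −6.4% to +6.7% |
| 48, 72, 168, 336 | −7.0% to +7.5% | −6.9% to +7.5% |
| 72, 168, 336 | −8.3% to +8.8% | −8.1% to +9.1% |
| 48, 72, 168 | −9.8% to +10.3% | −9.3% to +10.8% |
| 24, 36, 48, 72 | −11.3% to +11.9% | −10.6% to +12.8% |
| 168, 336 | −14.8% to +15.3% | −13.3% to +17.4% |
| 36, 48, 72 | −16.2% to +16.7% | −14.3% to +19.4% |

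Counting time from the start of the infusion instead of its end adds about one percentage point to the last row. A line through 48 and 72 h alone would give about 25%; I leave it out as not a credible terminal fit.

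**Step 3: a consistent, plausible deviation.** The infusion ends at 14:00 and visits are at 09:00, so Day 8 is at 163 h and Day 15 at 331 h, both within 5% of nominal. The earlier samples are on time.

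- 72/168/336 h: (−120×72 − 24×163 + 144×331)/35,712 = 35,112/35,712 = 0.983, so ke is 1.7% low.
- 48/72/168 h: (−48×48 − 24×72 + 72×163)/8,064 = 7,704/8,064 = 0.955, so ke is 4.5% low.
- 72/168 h only: (163 − 72)/(168 − 72) = 91/96 = 0.948, so ke is 5.2% low.

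**Step 4: Vd.** Vd = Dose/(ke × AUC(0-∞)). AUC also changes, so the result depends on the half-life. With a linear-log trapezoidal AUC, three terminal points and assumed half-lives, the worst case is:

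- With Day 8 and Day 15 samples: about 12% at 31 h, 10% at 72 h, 7% at 120 h and 4% at 240 h.
- Without them: about 20% at 15 h and 15% at 31 h.

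AUC(0-∞) itself moves by at most about 6%.

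**The case against.** The strongest reply is that the option needs a planned time, and the Day 8 and Day 15 samples have none in hours. On a strict reading the test cannot be applied to them and the default of actual times stands. That is right as far as it goes: a reader might infer that the protocol itself permits 8 h and 17 h, but those figures depend on assumed nominal hours. What remains is that the text does not say the option is closed for these samples, and it still applies to every sample up to 72 h.

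Second, the late samples may not determine the slope at all. The only half-life in the documents is 15 to 31 h in monkeys (Protocol 6.2.2.2). On that figure, 168 h is about 5 to 11 half-lives, and the concentration may be below quantification. Protocol 6.2.2.3.2 also reports long-lasting profiles in some animals, and no human half-life is given, so this cannot be settled. It does not help the rule: a fit limited to 36-72 h gives the largest worst-case shifts in the table.

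Third, the worst cases need opposing extreme deviations, which are unlikely for timed samples taken during or soon after the Cycle 1 hospital stay. That stands, and typical errors will be smaller.

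Fourth, deleting the option does not make the analysis fully reproducible, because terminal points are still chosen by eye and values below quantification may be reset case by case. That also stands. Those are separate sources of variation and no reason to keep this one.

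**Conclusion.** The point holds as a minor, cost-free improvement. The option lacks a criterion, an absolute cap and a nominal hour for Days 8 and 15, and it can only make the times less accurate. Under mono-exponential decline the worst-case shift in ke is 8-9% with 72/168/336 h and about 7% to 17% with the other sets examined; half-life shifts by up to about 19%.

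Three stronger readings are not supported:

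- A reader might take 9% as a ceiling for ke, half-life and Vd together. It belongs to one set of terminal points. Vd has no single bound, since its shift depends on the half-life and on which samples exist.
- A reader might infer a 5% error in every patient with a morning visit. That needs a slope resting on 72 h and Day 8; with Day 15 included it is about 2%.
- A reader might infer a threat to the dose decision. The Cohort Review Committee does look at PK (Protocol 8.7), but the MTD and DLT definitions (Protocol 8.5.5.1) do not use these parameters. PK is a secondary objective and is summarised descriptively.

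**What to change.** Delete the sentence in Protocol 8.5.3 that allows planned times within 5%. Alternatively, state in the SAP that recorded infusion start and end times and recorded sample times are always used when available. Keep planned times only for an unknown or missing actual time, as the following sentence already provides.

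This costs nothing in patients, visits or data. Actual times are already the default, and Protocol 8.4.4 already requires infusion start and end to be recorded. The change can be made at the analysis stage, and concentration summaries by scheduled time point (Protocol 9.3.2) are not affected. It removes this source of error wherever the actual time is known.

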8.5.4 Safety Assessment

Safety and tolerability endpoints will be derived from the following measurements/evaluations:

- Incidence, intensity, CTCAE version 4.03 grading, seriousness, and treatment-causality of Treatment Emergent Adverse Events (TEAEs).
- Frequency of clinically significant abnormalities in:
 - Physical examination and vital signs.
 - Safety laboratory tests.
 - 12-lead ECG record.
 - Urinalysis.

8.5.4.1 Medical History

Complete medical history will be collected during the Screening Period in order to obtain all information necessary to confirm the study inclusion and exclusion criteria.

General medical history shall include all the diseases (excluding solid tumors for Step 1 and NHL for Step 2) and conditions, either chronic or not, which are needed to assess the compliance with inclusion/exclusion criteria and those which are relevant according to the Investigator.

For Step 1, the solid tumors specific medical history will include: date of onset of tumor, organ of primary tumor, histological type, grade, date of diagnosis of metastatic disease, presence of hepatic and bone metastasis, number and type of previous treatments, and duration of the response to the last treatment.

For Step 2, the NHL specific medical history will include: date of onset of NHL, cell of origin, clinical behaviour, histological type, liver or bone extranodal spread, number and type of previous treatments relapsed or refractory status following the last NHL treatment, and duration of the response to the last treatment. General medical history shall be collected starting from 30 days prior to screening.

For both Step 1 and Step 2, specific medical history shall be collected starting from the tumor/NHL onset date.

8.5.4.2 Physical Examinations and Vital signs

A complete physical examination will be performed at Screening, at each day of Visit 1, at Visit 2, at Visit 3 and at the End of Study Visit, which will include a general appearance observation and a complete exam of the following body systems/areas: Head, Eyes, Ears, Nose and Throat (HEENT)/Neck, Lymph Nodes, Thyroid, Abdomen, Skin, Cardiovascular, Respiratory, Gastrointestinal, Neurological, and Musculoskeletal/Extremities.

Vital signs will be recorded throughout the study at Screening, at each day of Visit 1, at Visit 2, at Visit 3 and at the End of Study Visit. At Visit 1, vital signs should be measured prior to study drug administration and every 15 minutes at Cycle 1 and every 30 minutes starting from Cycle 2 during the first hour of study drug administration and then at every hour until the end of the infusion. In case of temporary infusion interruption, vital signs should be collected every 15 minutes until the first hour post-infusion re-start and then every hour until the end of infusion (or until 1-hour after the permanent infusion interruption).

The following parameters will be measured:

- Heart rate (HR; beats / min)
- Blood pressure (BP; systolic and diastolic, mmHg)
- Breathing rate (BR; breaths / min)
- Body temperature (T; °C).

8.5.4.3 Weight measurement

Body weight (to the nearest 0.1 kilogram [kg] in indoor clothing, but without shoes) will be measured during screening period and at study drug administration visits.

8.5.4.4 PS Evaluation

Performance Status Evaluation will be performed throughout the study at Screening, at Visit 1 prior to study drug administration, at Visit 2, at Visit 3 and at the End of Study Visit using the ECOG status (see Table 3).

Table 3: ECOG Performance Status

| Grade | ECOG |
|-------|---|
| 0 | Fully active, able to carry on all pre-disease performance without restriction. |

| | |
|---|--|
| 1 | Restricted in physically strenuous activity but ambulatory and able to carry out work of a light or sedentary nature, e.g., light house work, office work. |
| 2 | Ambulatory and capable of all selfcare but unable to carry out any work activities. Up and about more than 50% of waking hours. |
| 3 | Capable of only limited selfcare, confined to bed or chair more than 50% of waking hours. |
| 4 | Completely disabled. Cannot carry on any selfcare. Totally confined to bed or chair. |
| 5 | Dead. |

